4.4. Other Exploratory Endpoints

• Markers of bone turnover:

Will be analyzed for the randomized phase as described for the sex hormones and components of fat and glucose metabolism in Section 4.3.1.2.

• Physical function measures:

Will be summarized graphically as described for the FACT-P subscale in Section 4.3.1.2. The scoring procedures for PROMIS physical function questionnaires are elaborated in Appendix 3: Scoring for PROMIS.

4.5. Safety Analyses

All safety analyses will be descriptive and will be performed on the safety population. Safety data will be summarized descriptively for the lead-in phase and by treatment group for the randomized phase.

Page: 17 of 31

All AEs will be coded using the latest version prior to database lock of the Medical Dictionary for Regulatory Activities (MedDRA).

NOTE: AEs will be presented with their worst NCI-CTCAE grade.

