Results from the ARAMIS study led to the Food and Drug Administration (FDA), European Medicine Agency (EMA) and other regulatory authorities' approval of darolutamide for the treatment of men with nmCRPC.

Darolutamide is also being investigated in the metastatic hormone-sensitive prostate cancer. ARASENS is a randomized phase 3 study assessing the combination of ADT and docetaxel with or without darolutamide in mHSPC that has completed enrollment (Smith et al. 2022). ARANOTE is an ongoing study comparing the efficacy and safety of darolutamide and ADT versus ADT alone in mHSPC (Haresh et al. 2022).

Men in early stage of prostate cancer are concerned about the side-effects related to the ADT, therefore, optimizing treatment is of high importance to patients and caregivers. Drug induced adverse events may lead to a reduced quality of life, hence, treatments with favorable safety profiles could fulfill a medical need by providing an alternative to treatment with ADT.

Due to the fact that darolutamide is potent antiandrogen with strong efficacy and favorable safety and tolerability, there is rationale to study darolutamide in men with experiencing BCR prostate cancer. The available safety and efficacy data suggest that patients who participate in this trial are not placed at undue risk. Overall, the benefit/risk assessment for darolutamide monotherapy for hormone-naïve PC patients is favorable.

Cases of idiosyncratic drug-induced liver injury (DILI) with increases in ALT and/or AST to ≥ 5 and ≥ 20 x ULN, including with concomitant bilirubin elevation > 2x ULN, have been reported with darolutamide. Liver function tests abnormalities were reversible upon darolutamide discontinuation. Please see Section 6.2 and Section 7.1.

Page: 34 of 86

3. Objectives and Endpoints

Table 3-1: Lead-in Phase Objectives and Endpoints

Objectives	Endpoints
Primary	
To evaluate the impact of darolutamide monotherapy on serum testosterone level over a 12-week intervention period	Change in serum testosterone level from baseline to week 12
Secondary	
To evaluate the impact of darolutamide monotherapy on serum testosterone level over the course of a 52-week intervention period	Change in serum testosterone level from baseline at week 24 and 52
Assess PSA response rate	Serum PSA Week 4, 12, 24, 36, 52
To assess safety of darolutamide monotherapy in patients with hormone-naïve prostate Cancer with BCR	AE assessments using NCI CTCAE (v.5.0)

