8.8.3 Clinical Safety Laboratory Assessments

See Appendix 2 (Section 10.2) for the list of clinical laboratory tests to be performed and refer to the SoA (Section 1.5) for the timing and frequency.

The investigator must review the laboratory report, document this review, and record any clinically relevant changes occurring during the study in the AE section of the CRF. The laboratory reports must be filed with the source documents. Clinically relevant abnormal laboratory values or test results must be identified through a review of values outside of normal ranges/clinical notable ranges, significant changes from baseline or the previous visit, or values which are considered to be non-typical in patient with underlying disease.

All laboratory tests with values considered clinically relevant abnormal during participation in the study or within 30 days after the last dose of study intervention should be repeated until the values return to normal or baseline or are no longer considered clinically significant by the investigator or medical monitor. All protocol-required laboratory assessments, as defined in Appendix 2, Section 10.2, must be conducted in accordance with the SoA (Section 1.5).

If laboratory values from non-protocol specified laboratory assessments performed at the institution's local laboratory require a change in participant management or are considered clinically relevant by the investigator (e.g., SAE or AE or dose modification), then the results must be recorded in the CRF.

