9.4.4 Safety Analyses

All safety analyses will be descriptive and will be performed on the safety population. Safety data will be summarized descriptively for the lead-in phase and by treatment group for the randomized phase.

All AEs will be coded using the latest version prior to data base lock of the Medical Dictionary for Regulatory Activities (MedDRA).

Further details on safety analyses will be described in the SAP.

NOTE: AEs and safety lab parameters will be presented with their worst NCI-CTCAE grade.

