		Section 4.1.3: Remove 'within +/- 7 days of scheduled date'	Account for baseline measures done outside the window		
		Section 4.1.3: Clarify the nearest measure prior to the study drug administration date will be used for baseline	To include the baseline measures recorded in the 'Unscheduled' visit CRF pages		
		Section 4.1.3: Revise the logic to choose the measurement for the analysis	Remove ambiguity around 'scheduled date' and to include 'unscheduled' pos baseline measurement incase scheduled visits do not exist		
		Section 4.2.1: Remove 'darolutamide' from the primary analysis timepoint for randomized phase	Align with protocol v2.0 that last participant could be on either arm in randomized phase		
		Section 4.3.1.1 Change 'absolute' PSA response to 'Undetectable' PSA response, and 50% and 90% 'relative' PSA response to PSA50, PSA90.	Align with terminologies commonly used in other literature		
		Section 4.3.1.1 Remove relative 30% PSA response (PSA30)	To focus on PSA50 and PSA90 since response rate in mHSPC is very high		
		Section 4.3.1.1 Add 0.2 ng/mL detection limit value to PSA response rates definitions	Clarify detection limit		
		Section 4.3.1.1 Add Breast enlargement, Breast	Summarize all AEs classified as feminizing side-effects		
		mass, Breast swelling in gynecomastia Section 4.3.1.1 Add analysis of AEs of special	Summarize common AEs associated		
		Section 4.3.1.2: Add 'and a Toeplitz covariance structure' to the SAS PROC MIXED details	with ARI treatment Align with protocol v2.0		

Page: 5 of 31

ARAMON V3.0

_	1		
		Section 4.5: Remove language related to	Laboratory measures are not graded in
		grading of laboratory measures	this study
		Section 4.5.2 Remove TEAEs with incidence of	Not meaningful with the sample size of
		at least 5% table	the study
		Section 4.5.2 Add drug related TEAEs; add a	Elaborate safety findings
		comprehensive list of safety tables planned	
		Section 4.6.1: Add free testosterone as	Explore the treatment effect of
		exploratory analysis for lead-in phase primary	darolutamide on free testosterone
		analysis	
		Section 4.6.1: Remove FACT-P and exploratory	Prioritizing the important endpoints for
		endpoints from lead-in primary analysis	decision making to go into the
			randomized phase
		Section 6.1.1: Add Discontinued from treatment	Align with clarification on active follow-
		along with the primary reason for discontinuation	up in protocol v2.0
		in place of participants continued after treatment	

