All grades of the feminizing side effects of gynecomastia (including breast enlargement, breast mass, breast swelling), breast tenderness/pain, nipple pain, and hot flush will be summarized using frequencies and percentages. Incidence of AEs of special topics (Bone fractures excluding pathological fractures, Cerebral ischemia, Diabetes mellitus and Hyperglycaemia, Fall, Fatigue/ asthenic conditions, Weight decreased, Rash, Seizure, Hypertension, Vasodilatation and flushing, Mental impairment disorders, Depressed mood disorders, Breast disorders/gynecomastia, Cardiac disorders, Cerebral and intracranial hemorrhage) associated with ARI treatment will also be presented.

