4.8. Changes to Protocol-planned Analyses

There are no changes to the analyses described in the protocol.

ARAMON V3.0 Page: 20 of 31

5. Sample Size Determination

The sample sizes corresponding to the planned analysis methodology are provided below.

Lead-in Phase

Approximately 25 participants will be assigned to darolutamide to achieve at least 20 evaluable participants. This sample size will help estimate the mean percent change in serum testosterone level at 12 weeks with a 95% confidence interval having a half-width of no more than 25%, assuming a true mean percent increase of less than 45% and a standard deviation of 65%. This assessment uses a log normal distribution for percent change.

Randomized Phase

Contingent on the results of the evaluation in Section 1.2.1, the randomized phase statistical assumptions may be revised, or the study could be terminated after lead-in.

Should the study continue to the Randomized phase unmodified, a maximum of 40 participants (20 per arm) will be randomly assigned to study treatment (darolutamide or enzalutamide) such that approximately 34 evaluable participants complete the study. The randomized stage will require a sample size of 20 per group to provide 85% power to test the null hypothesis of no difference between groups on mean percent change at the two-sided 0.05 level. This assessment is based on a mean percent change in Testosterone from baseline and Standard Deviation for the Darolutamide arm of 45% and 65% versus 110% and 75% respectively for Enzalutamide and assumes a log normal distribution for percent change.

ARAMON V3.0 Page: 21 of 31

6. Supporting Documentation

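### SAP 4.5 drops the protocol's worst-grade laboratory presentation without declaring the change, so no summary named in the SAP shows how often liver tests rose

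*SAP*

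**What the plan says.** Protocol 9.4.4 ends its safety section with "NOTE: AEs and safety lab parameters will be presented with their worst NCI-CTCAE grade". It leaves the rest to the SAP: "Further details on safety analyses will be described in the SAP".

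SAP 4.5 carries the corresponding note with the laboratory half gone: "NOTE: AEs will be presented with their worst NCI-CTCAE grade". Its only subsections are exposure (4.5.1) and adverse events (4.5.2). The SAP Version History (version 2.0, 18 JAN 2024) records that the laboratory grading language was removed and gives as the reason "Laboratory measures are not graded in" this study. SAP 4.8 nevertheless says "There are no changes to the analyses described in the protocol", and SAP 1 says the same of protocol amendment 1.0.

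On the liver, Protocol 2.3 states: "Cases of idiosyncratic drug-induced liver injury (DILI) with increases in ALT and/or AST" have been reported with darolutamide. The Summary of Protocol Changes lists this as newly identified safety data. Table 6-1 sets out actions for ALT/AST increase by CTCAE grade and by multiples of ULN.

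**The concern.** A protocol-planned analysis has been removed while the section meant to disclose such removals says there are none. Someone relying on SAP 4.8 would expect graded laboratory tables in the report and would not find them among the outputs that the SAP names.

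The gap falls where the protocol has just added a risk. Liver injury is recognised first from ALT, AST, bilirubin and INR. If these values are not summarized, the report cannot state from a planned table how many men in each phase or arm exceeded a given multiple of ULN. It could state only how many had an event that an investigator chose, or was required, to report. The trial is open-label, so that choice is made with knowledge of treatment.

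**Working it through.** There is no plan figure to reproduce. The check sets the texts side by side and counts the outputs.

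**1. The commitment and its removal.**

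| Item | Protocol | SAP |
|---|---|---|
| AEs by worst grade | 9.4.4: yes | 4.5: yes |
| Safety laboratory parameters by worst grade | 9.4.4: yes | 4.5: absent |
| Declared as a change | n/a | 4.8 and 1: none declared |

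Both sides are current text. The Version History is needed only to show that the removal was deliberate.

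**2. The outputs named in SAP 4.5.2.** 13 general AE/SAE summaries + 9 feminizing-effect summaries + 1 special-topic summary = 23. None is a laboratory summary. The special-topic list in SAP 4.3.1.1 begins "Incidence of AEs of special topics (Bone fractures excluding pathological fractures, Cerebral ischemia, Diabetes mellitus and Hyperglycaemia, Fall" and has 15 entries, none hepatic. The one hepatic output elsewhere is a category at baseline (SAP 6.1.2). Fasting glucose, lipids and hormones are analysed as secondary endpoints, but not by grade; liver tests and haematology are not among them.

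**3. The data available.** Protocol Tables 1-3 and 1-4 schedule liver chemistry and haematology at baseline, weeks 4, 12, 24, 36 and 52, and the end-of-treatment visit. That is six post-baseline time points with no summary named in the SAP.

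**4. The reason given.** Table 6-1 has separate rows for ALT/AST increase at Grades 0-1 and Grades 2-3-4, and Protocol 6.2.2.1 equates Grade 2 or higher with ALT/AST above 3 x ULN. Grade is thus tied to the laboratory value for the tests that matter here. The statement that laboratory measures are not graded sits badly with this.

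**5. What still reaches a table.**
- Protocol 8.8.3 requires the investigator to "record any clinically relevant changes occurring during the study in the AE section of the CRF". Such events appear in the SAP 4.5.2 tables by preferred term, grade, relatedness, seriousness and discontinuation.
- Protocol Table 10-1 note 1 makes ALT at or above 3 x ULN with bilirubin at or above 2 x ULN (more than 35% direct), or with INR above 1.5 if measured, a mandatory SAE. This rule is defined by laboratory values, not by judgement of relevance.
- SAP 4.1.2 lists all data by participant.

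**6. What does not.** Isolated ALT or AST above 3, 5 or 8 x ULN is not automatically an SAE. The Table 10-1 rule is worded for ALT, whereas Table 6-1 uses ALT or AST. AE tables by preferred term do not show a transaminase rise and a bilirubin or INR rise jointly in the same man.

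**The case against.** The strongest reply is that liver injury remains assessable. Hepatic events recorded as AEs are tabulated in detail, the most serious laboratory combination is a mandatory SAE, SAP 6.1.1 gives reasons for treatment discontinuation, and every value is listed. This stands. A reader might infer from the missing tables that liver injury cannot be assessed at all, or that a raised liver test reaches a table only through an investigator's judgement. The documents support neither inference. What is lost is the summary of isolated or unreported elevations.

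Second, the removal was logged with a reason, so it was not an oversight. This also stands, but a Version History entry does not make SAP 4.8 correct. It could be argued that Table 6-1 grades the AE of ALT/AST increase rather than the measurement. Protocol 6.2.2.1, however, defines that grade by the measured value.

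Third, SAP 1 places table specifications in a separate document, and SAP 4.5 says in general terms that safety data will be summarized descriptively. Laboratory tables may therefore exist in those specifications, which were not available. They would not reconcile SAP 4.5 and 4.8 with Protocol 9.4.4.

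Fourth, Protocol 8.7 describes the safety assessments as investigator-recorded AEs, 8.7.7 names no AEs of special interest, and nothing requires a hepatic special topic. This stands: that topic is a preference. It does not cancel the explicit laboratory commitment in 9.4.4.

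**Conclusion.** The point holds as an undeclared departure from the protocol with a limited but real effect on safety reporting. Protocol 9.4.4 and SAP 4.5 disagree, and the no-change statements in SAP 4.8 and SAP 1 are incorrect on this item. As the SAP is written, liver safety rests on investigator-reported AEs, SAEs (including the mandatory rule for possible Hy's Law cases) and listings. None of the 23 listed summaries shows laboratory grades or counts crossing the protocol's liver thresholds.

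This affects every treated man: about 25 planned in the lead-in phase and, if the randomized phase proceeds, 20 per arm. A reader might want to pool the 25 + 20 = 45 darolutamide participants into one event-rate bound. The documents do not support that: the phases are to be analysed separately, the randomized phase is conditional, and safety is descriptive.

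The conclusion rests on the SAP text alone, with the output specifications unseen.

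**What to change.** In SAP 4.5:

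1. Restore the presentation of haematology and chemistry by worst CTCAE grade.
2. Add one descriptive liver-chemistry table, separately by phase and by arm in the randomized phase. Count participants with worst post-baseline ALT or AST above 3, 5 and 8 x ULN, and those with ALT or AST above 3 x ULN together with total bilirubin above 2 x ULN, or INR above 1.5 where INR was measured. Use all post-baseline values, unscheduled ones included, because SAP 4.1.3 otherwise prefers the scheduled visit.
3. Label the rows as laboratory value categories, not as the Table 6-1 discontinuation criteria. Table 6-1 also requires more than two weeks' duration for the 5 x ULN criterion and has a criterion based on symptoms or eosinophilia. Scheduled values alone cannot supply these: after week 4 the scheduled on-treatment draws are 8 to 16 weeks apart. INR is specified at screening and after an ALT/AST rise, not at each visit.

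If any part is not restored, declare and justify it in SAP 4.8 as a change from Protocol 9.4.4, and correct the matching sentence in SAP 1. A hepatic special topic is optional.

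The cost is SAP wording and a few extra standard tables from data the protocol already collects. No protocol amendment, visit or participant is added.

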4.5.1 Extent of Exposure

Study drug is defined as darolutamide for the lead-in, and darolutamide and enzalutamide for the randomized phase. As a rule, trailing "0 mg" records, which are not followed by any positive amount of drug, will not be included in the calculation of any drug duration or amount. Similarly, trailing "drug interruptions" will not be used in statistical tables. Interruption becoming permanent study treatment discontinuation is not accounted as an interruption.

Descriptive statistical summaries will be provided for the for the following variables:

• Overall time under treatment (or treatment duration)

Including time off drug and dose interruptions. It will be calculated in days and presented in months as (date of the last dose of any study treatment – date of the first dose of any study treatment + 1) / 30.44.

Actual dose per day

Actual dose per day = total amount of dose / number of days with intake > 0

• Total amount of dose

Total amount of dose = sum of dose received over total time under treatment

• Percent of planned dose received.

Percent of planned dose received = total amount of dose [mg] / planned dose [mg] * 100%; planned dose is sum of the intended initial dose according to protocol over total time under treatment.

4.5.2 Adverse Events

Treatment-emergent AE (TEAE) is defined as any event arising or worsening after the first dose of study drug until 30 days after the last dose of study drug.

An overview of TEAEs will be summarized for the appropriate safety analysis set at the three data cuts. The following summaries will be done.

- Overview of TEAEs
- TEAEs by MedDRA ad worst CTCAE grade
- TEAEs by MedDRA ad worst CTCAE grade 3, 4 or 5
- TEAEs: number of subjects by primary SOC and PT
- TEAEs leading to permanent discontinuation of study drug: number of subjects by primary SOC and PT
- Number of subjects with TEAE by PT in decreasing order
- Drug-related TEAEs: number of subjects by primary SOC and PT

• Drug-related TEAEs leading to permanent discontinuation of study drug: number of subjects by primary SOC and PT

Page: 18 of 31

- Number of subjects with drug-related TEAE by PT in decreasing order
- SAEs: number of subjects by primary SOC and PT
- TESAEs: number of subjects by primary SOC and PT
- Drug-related TESAEs: number of subjects by primary SOC and PT
- TE non-SAEs (excluding TESAEs): number of subjects by primary SOC and PT

Additionally, feminizing side effects as described in Section 4.3, will be summarized by

- Overview of TEAEs of feminizing side effects
- Number of subjects with TEAEs of feminizing side effects by PT in decreasing order
- Treatment-emergent study drug-related adverse events of feminizing side effects by MedDRA SOC and PT and worst CTCAE grade
- Number of subjects with TEAEs of feminizing side effects leading to permanent discontinuation of study drug by PT in decreasing order
- Number of subjects with drug-related TEAEs of feminizing side effects by PT in decreasing order
- Number of subjects with drug-related TEAEs of feminizing side effects leading to permanent discontinuation of study drug by PT in decreasing order
- SAEs of feminizing side effects: number of subjects by primary SOC and PT
- TESAEs of feminizing side effects: number of subjects by primary SOC and PT
- Drug-related TESAEs of feminizing side effects: number of subjects by primary SOC and PT

AEs of special topics will be summarized by

• Number of subjects with special topics for adverse events

4.6. Other Analyses

4.6.1 Lead-in Phase Analyses

For the lead-in phase primary analysis: change in free testosterone from baseline to week 12, will be analyzed similar to serum testosterone. PSA response analysis summarized in section 4.3.1.1 will be repeated with non-confirmed PSA responses. Data collected on the CRF for Serum and Free testosterone, PSA, sex hormones, fat and glucose metabolism will be summarized in spider plots to support any changes to data collection for the randomized phase, or for additional support of the randomized phase findings. The median treatment duration will be presented in months. For subjects ended treatment before the data cut-off date, duration will be 'last dose date – first dose day +1'. For subjects on treatment by the day of data cut-off, the duration will be 'data cutoff date – first dose day +1'.

For the lead-in phase final analysis: for the sex hormones and the components of fat and glucose metabolism at weeks 4, 12, 24 and 52, the differences between the log transformed

ARAMON V3.0 Page: 19 of 31

data at the visit and baseline will be estimated with 95% Confidence Intervals using SAS PROC MIXED with the ESTIMATE statement. These will be transformed to mean percent change and 95% confidence intervals using the same steps as for the primary analysis in the lead-in phase. SAS code will be similar to that shown in Appendix 5: Lead-in phase analysis for natural logarithm transformed Testosterone and other endpoints using the log transformation. Sex hormones and fat and glucose metabolism endpoints will be depicted graphically over time with 95% confidence intervals at each visit.

The FACT-P prostate cancer subscale scores will be summarized at each visit using PROC Mixed with the ESTIMATE statement and depicted graphically over time with 95% confidence intervals at each visit.

The physical function scores will be summarized graphically using the methods described above for FACT-P.

